6.2.11 WEEK 40 PHONE CALL

The following study evaluations will be performed on Week 40 ± 2 weeks via a phone call:

• AE/SAE assessment

- Review of histology results as read by PAC from Week 36
- Completion of quality of life questions will asked to subjects enrolled in US, Canada, Mexico, Germany and UK only
- PRO questionnaires (SF-36 and EQ-5D-5L) completion 8-14 days post Week 40 by a subject by subjects enrolled in US, Canada, Mexico, Germany and UK only

6.2.12 WEEK 62

The following study evaluations will be performed on Week 62 ± 2 weeks:

- Targeted physical assessment
- Vital Signs
- Urine pregnancy test
- ThinPrep[™] sample for HPV typing and pap smear (subject should be requested to abstain from any sexual activity and refrain from use of douching or vaginal lubricants/medication for a period of 24 hours prior to sample collection)
- Colposcopy (lesion photography should be attempted at least once)

6.2.13 **WEEK 88**

The following study evaluations will be performed on Week 88 ± 2 weeks:

- Full Physical Exam
- Vital Signs
- Socio-Behavioral Assessment (change in smoking alcohol intake or recreational drug use from baseline)
- Urine pregnancy test
- ThinPrep[™] sample for HPV typing and pap smear (subject should be requested to abstain from sexual activity and refrain from use of douching or vaginal lubricants/medication for a period of 24 hours prior to sample collection)
- Oropharynx (OP) by oral rinse and vaginal swabs for HPV testing
- Colposcopy (lesion photography should be attempted at least once)
- PRO questionnaires (SF-36 and EQ-5D-5L) completion by a subject (if enrolled in US, Canada, Mexico, Germany and UK only)

6.3 EVALUATIONS AND PROCEDURES

6.3.1 INFORMED CONSENT

All subjects must sign the informed consent prior to any study related procedures being performed (i.e., prior to any screening activities). The informed consent documentation must be in accordance with applicable regulations and GCP. Qualified study personnel will meet with prospective study subjects, explain the study, and provide them with an informed consent form (ICF) that describes the screening tests, eligibility criteria for entering the study, study treatments and follow-up procedures, in a language understandable to the subject. Explanation of the study includes, but is not limited to, study objectives, potential benefits and risks, discomforts/inconveniences, and the subject's rights and responsibilities. The subject is then requested to sign and date the ICF. A copy

of the signed informed consent documentation must be provided to the subject. The qualified study personnel will document the process of obtaining informed consent within the source record. Signed ICFs are maintained in the subject's source records and must be accessible for verification at any time.

6.3.2 ASSIGNMENT OF SUBJECT IDENTIFICATION NUMBERS

Each subject who consents will be assigned a unique subject identification number (SID), which identifies the subject for all study-related procedures. SIDs are a combination of a up to two alpha letters study code, two alpha letter Country code, two digit site number, plus 3-digit subject number starting with (e.g.,). Once assigned, SIDs cannot be reused for any reason. Information regarding the SID and screen date must be documented on a Screening log/system and in the Interactive Response Technology (IXRS).

Subjects meeting eligibility criteria will be randomized by a computer generated allocation schedule.

6.3.3 SAFETY EVALUATIONS

6.3.3.1 Physical Exam

A full physical examination (PE) will be conducted during screening and study discharge. It will include an assessment of the following: general appearance, skin, head, eyes, ears, nose, and throat, and lymph nodes, and respiratory, cardiovascular, gastrointestinal, genitourinary, musculoskeletal, and neurological systems.

A targeted physical assessment will be performed at other visits as determined by the investigator or directed per subject complaints.

6.3.3.2 Vital Signs

Vital signs will be measured at specified visits and will include:

- Sitting systolic and diastolic blood pressures with subject sitting at rest for at least 5 minutes before measurement
- Respiration rate
- Heart rate
- Oral temperature measured with an automated thermometer

6.3.3.3 Weight and Height

Weight and height will be collected at screening in order to calculate the BMI. Weight will be collected on Day 0, Weeks 4 and 12.

6.3.3.4 Medical History

All relevant (as judged by the investigator) past and present conditions at screening, as well as prior surgical procedures will be recorded for the main body systems. The medical history will include a) any prior history of CIN diagnosed – with diagnosis date(s) and respective CIN level(s), and b) if treated previously for CIN, the respective treatment type(s) and date(s).

6.3.3.5 Socio-Behavioral Assessment

Socio-Behavioral Assessment, including self-reported smoking history, self-reported history of exposure to second-hand smoke, self-reported alcohol intake history, self-reported recreational drug use history, self-reported history of contraceptive use and type of contraceptive if known, reproductive history, history of prior cervical dysplasia, and pregnancy history will be obtained at Screening.

At Weeks 36 and 88, socio-behavioral assessment will be performed to document any change from screening.

6.3.3.6 Laboratory Evaluations

At screening, blood samples will be taken to be tested for serum chemistry and hematology.

Complete blood count (CBC):

- White blood cell (WBC) count with differential
- Red blood cell (RBC) count
- Hemoglobin, Hematocrit
- Platelet count

Serum Chemistry:

- Glucose
- Serum glutamic-pyruvic transaminase (SGPT)/Alanine aminotransferase (ALT)
- Blood urea nitrogen (BUN)
- Creatinine
- Electrolytes (Sodium, Potassium, Chloride, Carbon Dioxide or Bicarbonate)
- Creatine Phosphokinase (CPK)

Urinalysis (UA):

Urine samples will be tested at screening by dipstick for glucose, protein, and hematuria. If abnormal (presence of protein, hematuria, or glucose $\geq 1+$) a microscopic examination should be performed.

6.3.3.7 Demographics

Demographic information will be collected via self-report (unless noted otherwise), including the following:

- Age
- Race/ethnicity

6.3.3.8 Urine Pregnancy Testing

For subjects of reproductive potential, a negative spot urine pregnancy test is required prior to each study treatment, colposcopy and surgical excision.

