- 24. Prisoner or subject who is compulsorily detained (involuntarily incarcerated) for treatment of either a psychiatric or physical (i.e. infectious disease) illness;
- 25. Active military service personnel;
- 26. Study-related staff or family member of study-related staff;
- 27. Any illness or condition that in the opinion of the investigator may affect the safety of the subject or the evaluation of any study endpoint.

Table 1. Schedule of Events

	_	Weeks													
Tests	Screening (-10 weeks to -1 Day from Date of Biopsy)	Day 0	8-14 days post Day 0 Phone Call	4 (± 4 days)	8-14 days post Week 4 Phone Call	8 (± 4 days)	12 (± 4 days)	8-14 days post Week 12	15 (± 1 week)	28 (± 1 week)	36 (± 1 week)	40 (± 2 weeks) Phone call	62 (± 2 weeks)	88 (± 2 weeks)	
Informed consent	X														
Medical History	X														
Demographics	X														
Socio-behavioral ^a	X										X			X	
Inclusion / Exclusion	X	X													
Randomization		X													
Physical exam/assessment ^b	X	X		X		X	X		X	X	X		X	X	
Vital signs	X ^c	X		X		X	X		X	X	X		X	X	
Screening safety ^d	X														
Pregnancy Test ^e	X	X		X			X		X	X	X		X	X	
HIV Antibody Testing	X														
Blood immunologic samples ^f	X	X				X			X^g		X				
Cervical Digene swabsi,j	X	X							X	X	X				
ThinPrep ^{™ h,i}	X	X				X			X	X	X		X	X	
Colposcopy, lesion photograph ^k	X ^l	X							X	X	X		X	X	
Ectocervical biopsy ^m	X										Xn				
Surgical excision ^m											Xn				
OP rinse, vaginal swabs		X									X			X	
Intra-anal swabs ^o		X									X				
Inject VGX-3100/Placebo		X		X			X								
Post treatment assessment		X	X	X	X	X	X	Xq	X						
AE/SAE assessment	X	X	X	X	X	X	X	X	X	X	X	X	X	X	
Distribute PDC		X		X			X								
Review PDC			X		X	X		Xq							
PROs ^p		X	X	X	X		X	X^q		X	X	X		X	

^a Socio-Behavioral assessments, e.g. self-reported smoking and alcohol history

b Full physical examination (PE) mandatory at screening and study discharge (Week 88), otherwise targeted physical assessment as determined by the Investigator or per subject complaints unless signs or symptoms dictate the need for a full PE;

^c Screening vital signs must include a measured height and weight. Weight will be collected on Day 0, Weeks 4 and 12;

- ^d Screening safety includes 12-Lead ECG, complete blood count (CBC), serum electrolytes, blood urea nitrogen (BUN), serum creatinine (Cr), serum glucose, serum ALT, serum CPK and urinalysis performed within 45 days prior to Day 0:

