- ^e For WOCBP, a negative spot urine pregnancy test is required at screening and prior to each study treatment, colposcopy and surgical excision;
- f At least 34 mL [4 x 8.5 mL yellow (ACD) tubes] whole blood per time point and 8 mL serum per time point at Screening, Day 0 and Week 8 (4 ml serum per time point at Week 15 and 36). A total of at least 68 mL of whole blood and 16 ml serum should be collected prior to dosing on Day 0.
- ^g At least 51 mL [6 x 8.5 mL yellow (ACD) tubes] whole blood and 4 mL serum should be collected at Week 15;
- h HPV genotyping and Pap smears are performed on the same ThinPrep[™] cervical specimen:
- ¹ Request that the subject abstain from sexual activity and refrain from use of douching or vaginal lubricants/medication for a period of 24 hours prior to cervical specimen collection;
- j Collected prior to the ThinPrep[™] sample;
- ^k A photograph of the lesion with at least one attempt should done as follows: Acetic acid should first be applied to the cervix then photographs of the cervix and the associated lesion should be photographed prior to and after biopsies (if applicable) and at all colposcopic examinations; if repeat photographs are sought, they should be done at the next protocol-specified colposcopy visit.
- Screening colposcopy is optional if adequate colposcopy was performed upon collection of initial biopsy;
- ^mScreening biopsy of the lesion should be collected as Paraffin-embedded cervical tissue, fresh cervical tissue, or H&E slides. Tissue to be analyzed for evidence of histopathologic regression will be obtained at Week 36 visit either by excision (e.g. LEEP, LLETZ, CKC) or by 4 Quadrant Biopsy or 4 Quadrant Biopsy with ECC based upon the assessment at Week 28 of cytology, HR HPV status, and colposcopic findings (See Tables 4 and 5);
- ⁿ Slides from biopsy and/or excised tissue must be reviewed by the PAC and residual cervical tissue from screening and/or Week 36 specimen(s) (paraffin blocks or unstained slides) may be used for immunohistochemistry (IHC) and HPV testing;
- ^o To be collected only if subject consents for intra-anal sample collection
- P One or both PRO questionnaires (i.e. SF-36 and EQ-5D-5L) will be completed by subjects enrolled in USA, Canada, Mexico, Germany and UK at multiple visits during the study. Additional quality of life questions will be asked at the Week 40 phone call. Refer to Section 6.8 for details

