1.3.2 POTENTIAL RISKS OF STUDY PARTICIPATION

A risk associated with VGX-3100 for the treatment of high grade cervical dysplasia are the injection site reactions related to the IM injection and/or electroporation. Based on the phase 1

and 2 clinical experience, the injection site reactions associated with the IM injection and electroporation are generally mild (e.g. erythema) and limited to a few days in duration at most.

A second risk is the "delay" in "definitive treatment" of the high grade cervical dysplasia and the "missed diagnosis" of an occult early invasive cervical cancer for the VGX-3100 non-responders or placebo recipients, who do not spontaneously regress. This risk is mitigated by careful serial cytology, HPV testing, and colposcopic exams, throughout the course of the study, and the well accepted understanding that cervical dysplasia progresses slowly, typically over years, which makes close, active follow-up possible. Also, only investigators who are experienced in the management of cervical cancer will be chosen, and they will have the option of performing additional, ad hoc colposcopic exams and cervical biopsies if they suspect potential disease progression.

A DSMB will also advise the Sponsor if it appears that the frequency of regression in the VGX-3100 group is unacceptably low compared to the placebo group. These measures should minimize the risk - even perhaps below that of standard care - of progression of the cervical HSIL and the risk of harboring an undiagnosed occult early invasive cervical cancer. All subjects with suggestion of residual disease will undergo excisional therapy (e.g. CKC, LLETZ, LEEP) at Week 36 as part of the efficacy assessment. Subjects whose cytology, HPV testing, ECC results (if applicable) and colposcopic exam suggest disease regression will undergo 4 quadrant biopsy or 4 quadrant biopsy with ECC (based upon Tables 4 & 5) to provide histopathologic confirmation of regression. In the Phase 2b study, the rate at which microinvasive cancer was found in larger surgical excision samples in subjects who had no evidence of invasive cancer by initial biopsy was 1.8%, (2/114 with specimens), which is consistent with and even lower than the rate of 6.7% that has been reported under standard of care settings [22].

1.3.3 POTENTIAL BENEFITS OF STUDY PARTICIPATION

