2.3 SAFETY MONITORING PLAN

Although cervical HSIL is thought to require years to progress to cervical cancer, subjects in the Phase 2b study were followed closely throughout. HPV testing (Weeks 14 and 24), cytology (Week 14) and colposcopy (Week 24) were all mandatory during the observation period prior to obtaining tissue for determination of the primary histologic endpoint at Week 36. Investigators were also instructed to perform additional testing (including biopsy) if disease progression was suspected. These instances were infrequent as only 11 unscheduled biopsies were deemed necessary over the course of the Phase 2b study. In addition, the rate at which occult microinvasive cancer was discovered after 36 weeks was less frequent than what is reported in the literature [22]. Both observations would imply that the mandatory monitoring employed in the Phase 2b study was sufficient; however cervical disease will be monitored even more closely in this Phase 3 study. Colposcopy, cytology and HPV testing will be required at 8 to 14 week intervals throughout the observation period leading up to the primary endpoint 36 weeks after the first dose. Although less frequent monitoring may be adequate, the more frequent monitoring is designed to afford an even wider margin of safety and an opportunity to explore predictors of efficacy.

Safety monitoring will include:

• Local and systemic events for 7 days following each treatment as noted on a Participant Diary Card (PDC).

 All adverse events including SAEs, UADEs, and other unexpected AEs for the duration of the study;

In the Phase 2b study, the safety profile was carefully evaluated and treatment with VGX-3100 was well-tolerated based on observations through Week 88 in all subjects. The most common adverse events were administration-site reactions, which included pain, tenderness, erythema and swelling, and were generally mild and limited to a few days in duration. Only erythema showed a statistically higher incidence in VGX-3100 (78%) vs. placebo (57%) in the 7- and 28-day periods after a dose. One additional AE, sinusitis, was also statistically significantly increased over the course of the entire study period but resolved without sequelae in the VGX-3100 arm compared to the Placebo arm (10% vs. 0%).

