As outlined above, safety monitoring and visit frequency has been designed to take into account the potential risk of delay in the usual treatment of the high grade cervical dysplasia and also the potential for a missed diagnosis of an occult early invasive cervical cancer for the VGX-3100 non-responders or placebo recipients, who do not regress. Serial cytology, HPV testing, and colposcopic exams are applied throughout the course of the study with the well accepted understanding that cervical dysplasia progresses slowly, typically over years, which makes close, active follow-up possible. All subjects with suggestion of residual disease will undergo excisional therapy by LEEP or CKC at Week 36 as part of the efficacy assessment. Subjects whose cytology, HPV testing, ECC results (if applicable) and colposcopic exam suggest disease regression will undergo 4 quadrant biopsy or 4 quadrant biopsy with ECC (based upon Table 4 and 5) to provide histopathologic confirmation of regression. The use of a 4 quadrant biopsy in Phase 3 is a change from the approach used in Phase 2b to optimize the evaluation of histopathologic regression taking into consideration the inherent limitations of colposcopy and tissue biopsy samples in the absence of visible lesions [23].

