- PRO questionnaires (SF-36 and EQ-5D-5L) completion by a subject (if enrolled in US, Canada, Mexico, Germany and UK only)

6.2.8 **WEEK 15**

The following study evaluations will be performed on Week 15 \pm 1 week:

- Targeted physical assessment
- Vital signs
- Post-treatment injection site reaction assessment
- Urine pregnancy test
- Whole blood (at least 51 mL) and serum (at least 4 mL) for immunology
- 2 Digene cervical swab samples
- ThinPrep[™] sample for HPV typing and pap smear (subject should be instructed to abstain from any sexual activity and refrain from use of douching or vaginal lubricants/medication for a period of 24 hours prior to sample collection)
- Collect PDC

• Colposcopy (lesion photography should be attempted at least once)

6.2.9 **WEEK 28**

The following study evaluations/actions will be performed on Week 28 ± 1 week:

- Targeted physical assessment
- Vital signs
- Urine pregnancy test
- 2 Digene cervical swab samples
- ThinPrep[™] sample for HPV typing and pap smear (subject should be requested to abstain from any sexual activity and refrain from use of douching or vaginal lubricants/medication for a period of 24 hours prior to sample collection)
- Colposcopy (lesion photography should be attempted at least once) to assess for possible disease progression.
- ECC (only to be collected if ECC was done as part of Screening)
- PRO questionnaires (SF-36 and EQ-5D-5L) completion 8-14 days post Week 28 visit by a subject enrolled in US, Canada, Mexico, Germany and UK only

6.2.10 WEEK 36

The following study evaluations will be performed on Week 36 ± 1 week:

- Targeted physical assessment
- Vital signs
- Socio-Behavioral assessment (change in smoking alcohol intake or recreational drug use from baseline)
- Whole blood (at least 34 ml) and serum (at least 4 ml) for immunology
- Urine pregnancy test
- 2 Digene cervical swab samples
- ThinPrepTM sample for HPV typing and pap smear (subject should be requested to abstain from any sexual activity and refrain from use of douching or vaginal lubricants/medication for a period of 24 hours prior to sample collection)
- Oropharynx (OP) by oral rinse and vaginal swab for HPV testing
- Intra-anal swab (if subject has consented to intra-anal sampling) for HPV testing
- Colposcopy (lesion photography should be attempted at least once)

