7.1.9 PROCEDURES FOR DOCUMENTING PREGNANCY DURING STUDY

Subjects who are pregnant or expect to become pregnant during the course of the study up to Week 36 will be excluded from participation in the study. Should a subject become pregnant after receiving the first study treatment in the study, she will not be given any further study treatments. A Pregnancy Form will be completed by the site personnel and submitted to the sponsor or its designee within 24 hours after learning of the pregnancy. Site personnel will submit the Pregnancy Form to the Sponsor or its designee by fax, as described in Section 7.4.2.

The investigator will also report this event to the IRB within 24 hours of becoming aware of the pregnancy. Sites must request the subject's permission to query pregnancy outcome and follow each subject to determine the outcome of the pregnancy. Results will be summarized in the clinical study report (CSR).

Subjects who become pregnant at any point during the study will continue to be followed for safety assessments without receiving further study treatment. Procedures that are contraindicated during pregnancy, including additional treatments, must not be performed. Investigators should use clinical judgment regarding subsequent study-related blood collection based on the presence or absence of anemia in each subject.

All pregnancies that occur from the time of first study treatment through the follow up visits must be reported. The investigator will monitor the subject and follow the outcome of the pregnancy. If the end of the pregnancy occurs after the study has been completed, the outcome will be reported directly to the study team and the medical monitor.

7.2 METHODS AND TIMING OF THE COLLECTION AND RECORDING OF SAFETY DATA

Non-serious AEs and SAEs (and UADEs) will be collected for each subject from the time when informed consent is obtained through Week 88.

The sources of AEs cover:

- 1. The subject's response to questions about her health (a standard non-leading question such as 'How have you been feeling since your last visit?' is asked at each visit).
- 2. Symptoms spontaneously reported by the subject.
- 3. Evaluations and examinations where the findings are assessed by the investigator to be clinically significant changes or abnormalities.
- 4. Other information relating to the subject's health becoming known to the investigator (e.g. hospitalization).

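### A negative pregnancy test is a condition of each colposcopy, so read literally a woman who conceives on study loses the scheduled Week 15, 28 and 36 examinations, and section 7.1.9 does not say whether they continue

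*Protocol*

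**What the plan says.** All references are to protocol v5.0.

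- **The condition.** Section 6.3.3.8: "a negative spot urine pregnancy test is required prior to each study treatment, colposcopy and surgical excision". Table 1 footnote e adds screening: "a negative spot urine pregnancy test is required at screening and prior to each study treatment, colposcopy and surgical excision". Both ask for a negative result, not merely a test with a known result.
- **The examinations.** Section 6.12 schedules interval colposcopies at Day 0 and Weeks 15, 28, 36, 62 and 88. Section 2.3: "Colposcopy, cytology and HPV testing will be required at 8 to 14 week intervals throughout the observation period leading up to the primary endpoint". Section 6.2.9 gives the purpose of the Week 28 colposcopy: "to assess for possible disease progression".
- **Their role.** On delayed treatment and missed occult cancer, section 1.3.2 says: "This risk is mitigated by careful serial cytology, HPV testing, and colposcopic exams, throughout the course of the study". Section 2.3 says the same in its account of how safety monitoring was designed: "Serial cytology, HPV testing, and colposcopic exams are applied throughout the course of the study".
- **Pregnancy on study.** Section 7.1.9 stops dosing, keeps the subject in follow-up for safety assessments, and says: "Procedures that are contraindicated during pregnancy, including additional treatments, must not be performed". It does not mention colposcopy.

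**The concern.** The protocol sets serial colposcopy as a safeguard for women whose HSIL is left untreated until Week 36, and then makes each examination depend on a negative pregnancy test. A site that follows 6.3.3.8 and footnote e as written would stop scheduled colposcopy once a test is positive.

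The woman concerned may still have her lesion. Inclusion criterion 9 requires that a visible lesion remain after the screening biopsy, and section 2.1.1 takes the tissue that would show regression only at Week 36. Surgical excision at Week 36 is under the same condition, so definitive treatment may also be put off when routine colposcopy has ceased. What is at stake is the scheduled examination of a woman with no other warning sign.

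**Working it through.** **Step 1: where the condition has an effect.** From Table 1, between first dose and Week 36, the visits that carry a pregnancy test are:

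| Visit | Study treatment | Excision possible | Colposcopy |
|---|---|---|---|
| Week 4 | yes | no | no |
| Week 12 | yes | no | no |
| Week 15 | no | no | yes |
| Week 28 | no | no | yes |
| Week 36 | no | yes | yes |

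At Weeks 15 and 28, colposcopy is the only listed procedure that the condition can apply to, so the wording is not idle there. Day 0 is not at issue, because pregnancy is exclusionary (exclusion criterion 5).

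**Step 2: the texts side by side.**

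- 6.3.3.8 and footnote e: no negative result, no colposcopy; no exception.
- 2.3 and 6.12: colposcopy is required at those same visits; no exception for pregnancy.
- 7.1.9: follow-up continues and contraindicated procedures stop; colposcopy is placed in neither group.
- Section 6: waivers are refused except for immediate safety concerns, so a routine waiver is not a way out.

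For a pregnant subject, the first two cannot both be followed, and the third does not choose between them.

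**Step 3: how many women.** Inputs: 198 randomized (8.3); contraceptive failure below 1% per year with consistent, correct use until Week 36 (inclusion criterion 10c). Take all 198 as of childbearing potential and the failure rate at its ceiling:

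198 × 0.01 × 36/52 = 1.37 women conceiving before Week 36.

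The count is proportional to the failure rate. The documents give no rate for imperfect use; twice the ceiling, for example, would give 2 × 1.37 = 2.74.

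**Step 4: which examinations are lost.** Two assumptions are not in the documents: the test turns positive 2 weeks after conception, and the pregnancy continues past Week 36.

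| Conception | Colposcopies lost | Expected women |
|---|---|---|
| Day 0 to Week 13 | Weeks 15, 28, 36 | 198 × 0.01 × 13/52 = 0.495 |
| Weeks 13 to 26 | Weeks 28, 36 | 198 × 0.01 × 13/52 = 0.495 |
| Weeks 26 to 34 | Week 36 | 198 × 0.01 × 8/52 = 0.305 |

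The sum is about 1.29. With a lag of 1 week the first row becomes 198 × 0.01 × 14/52 = 0.533 and the sum 1.33. With a lag of 3 weeks it becomes 198 × 0.01 × 12/52 = 0.457 and the sum 1.26.

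A woman in the first row has no scheduled colposcopy from Day 0 to at least Week 36. The planned gaps are 15 − 0 = 15, 28 − 15 = 13 and 36 − 28 = 8 weeks.

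**The case against.** The strongest reply is that the condition may be deliberate caution. It stands in all three protocol versions shown, and v5.0 revised the pregnancy-reporting text without touching it. Whether colposcopy suits a pregnant woman is a clinical question that the documents do not answer. This stands, and it is why the fix leaves contraindication to the investigator. It does not remove the clash with 2.3 and 6.12.

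A reader might also infer that 6.3.3.8 contradicts 7.1.9, on the view that 7.1.9 bars contraindicated procedures and nothing else. The text does not support that. 7.1.9 has no such limiting word and never names colposcopy, and section 7.3 lists safety assessments as adverse events and injection-site review. A site could withhold colposcopy, continue adverse-event follow-up, and comply with both sections. The conflict lies with 2.3, 6.12 and 1.3.2; 7.1.9 is merely silent.

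Other safeguards remain. Cytology and HPV testing do not depend on the pregnancy test. Section 6.11 allows an ad hoc colposcopy and possible biopsy when a Pap smear suggests cancer. Section 6.12 allows unscheduled colposcopy on suspicion of worsening, and section 6.12.1 lets medical judgment override the schedule for a biopsy when progression is suspected. Section 4.3.2 permits withdrawal for obstetric or medical complications. These limit the harm, but they need a warning sign or complication, whereas the scheduled examination does not.

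**Conclusion.** The point holds as an unresolved conflict between the pregnancy-test condition (6.3.3.8, footnote e) and the required colposcopies (2.3, 6.12), with 7.1.9 failing to settle it. It is an optional but worthwhile clarification.

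About 1.4 of 198 women would be affected before Week 36, of whom about 0.5 would lose all three examinations. The total rests on contraception performing at the 1% ceiling with consistent, correct use: lower failure or fewer women of childbearing potential reduces it, imperfect use raises it. The split also rests on the assumed test lag and continuing pregnancy.

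The point is weaker at Weeks 62 and 88. The same condition applies there, and inclusion criterion 10c no longer requires contraception, but the Synopsis and section 2.4 describe long-term follow-up as safety, cytology and HPV testing.

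No effect on the efficacy conclusion should be inferred. A woman without an acceptable Week 36 histology specimen is a non-responder under 2.1.3, and missing outcomes count as failures under 8.15. Endpoint definitions, type I error rate and planned power are unchanged.

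**What to change.** - **6.3.3.8 and Table 1 footnote e:** limit the negative-result condition to screening, study treatment and surgical excision. Keep the pregnancy test at colposcopy visits for information only, and say that a positive result does not by itself cancel colposcopy without tissue sampling.
- **7.1.9:** state that scheduled colposcopy without tissue sampling, cytology and HPV testing continue in pregnant subjects unless the investigator judges them contraindicated, and that biopsy and ECC are left to the investigator's judgment.

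The cost is a wording amendment in three places, with no new visit, test or sample. The downside is continued pelvic examination in the few pregnant subjects, subject to the investigator's judgment.
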